3.4.2. Clinical Laboratory Tests

Statistical analysis of clinical laboratory tests, except for those as secondary endpoints (platelet count, LDH, creatinine, hemoglobin and haptoglobin) will be based on the results from central laboratories only. Results from central and local laboratories will be listed.

Summary statistics for the actual values and the change from baseline will be tabulated for laboratory results by dose, disease, and scheduled visit. Patients with laboratory values outside of the normal reference range at any post-baseline assessment will be summarized by dose and disease. Shift tables comparing the baseline NCI CTCAE grade to the worst post-baseline grade will be provided by dose and disease. These laboratory summary tables will exclude the laboratory tests that are the efficacy endpoints (Section 2.1).

Laboratory results may be presented graphically over the study scheduled visits, e.g., using box plots.

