7.3. Study Endpoints

7.3.1. Primary Endpoints

The co-primary endpoints are:

- Safety as assessed by adverse events (AEs), vital signs, ECGs, and clinical laboratory tests (includes patients with HSCT-TMA, aHUS, and TTP)
- For HSCT-TMA patients, response to OMS721 treatment. A responder is defined as a patient with HSCT-TMA who demonstrates improvement in laboratory TMA markers (platelet count and LDH) and clinical benefit (either improvement in organ function or reduction in transfusion burden). The specific criteria are defined as follows:
 - Improvement in laboratory TMA markers:
 - Platelet count:
 - For patients with baseline platelet count $\leq 20,000/\mu\text{L}$:
 - Tripling of baseline platelet count
and
 - Post baseline platelet count $> 30,000/\mu\text{L}$
and
 - No platelet transfusions 2 days before and on the day of the platelet count collection
 - For patients with baseline platelet count $> 20,000/\mu\text{L}$
 - Increase in platelet count $\geq 50\%$
and
 - Post baseline platelet count $> 75,000/\mu\text{L}$
and
 - No platelet transfusions 2 days before and on the day of the platelet count collection
 - and**
 - LDH:
 - $\text{LDH} < 1.5 \times \text{upper limit of normal (ULN)}$
 - and**
 - Improvement in clinical status:
 - Improvement in organ function as evidenced by any of the following:
 - Improvement in renal function:

CONFIDENTIAL

No use, disclosure or reproduction outside of Omeros without prior written authorization

- Reduction of creatinine > 40%
- or
- Creatinine < ULN and reduction of creatinine > 20%
- or
- Discontinuation of renal replacement therapy (RRT)

or

- Improvement in pulmonary function:
 - Extubation and discontinuation of ventilator support
- or
- Discontinuation of non-invasive mechanical ventilation (continuous positive pressure ventilation)

or

- Improvement in neurological function:
 - Improvement in reversible neurological conditions (e.g., cessation of seizures)
- or
- Stabilization of irreversible neurological conditions (e.g., stability of neurological deficits following stroke without further deterioration or subsequent strokes)

or

- Improvement in gastrointestinal function (gastrointestinal HSCT-TMA will require diagnosis by tissue biopsy):
 - Improvement measured by improvement in the gastrointestinal measures in the Mount Sinai Acute GVHD International Consortium (MAGIC) criteria

or

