13.2.9.3. Clinical Laboratory Results

Statistical analysis of clinical laboratory tests will be based on the results from central laboratories only. Results from central and local laboratories will be listed.

Summary statistics for the actual values and the change from baseline will be tabulated for laboratory results by dose, disease, and scheduled visit. Patients with laboratory values outside of the normal reference range at any post baseline assessment will be summarized by dose and disease. Shift tables comparing the baseline National Cancer Institute (NCI) CTCAE grade to the worst post baseline grade will be provided by dose and disease.

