2.5. Study Endpoint Baseline

In general, the baseline of a study endpoint is the last observation prior to the first study drug administration except for platelet count.

The baseline of a laboratory parameter will be based on the central laboratory values except for platelet count.

Platelet counts from the central laboratory are to be used in the calculation of baseline. If a central laboratory value is not available and its local laboratory value is available on the same collection date, the local laboratory value will be used. In addition, if there are at least 2 platelet count collections on the same date, the first one will be used.

Baseline platelet count is defined as the average of values obtained on different days in the week (including Day 1) prior to the first dose of OMS721. If more than 3 such values are available, then the 3 values that are most proximate to the first dose of OMS721 should be used. [Table 2](#) is an example of a baseline platelet count calculation.

Table 2: Example of Baseline Platelet Count Calculation

Study Day	Central Lab	Local Lab	Value to be used to Determine Baseline
-5	Yes	Yes	Not used
-4	Yes	Yes	Central lab
-3	No	Yes	Local lab
-2 (1 st)	No	Yes	Not used
-2 (2 nd)	Yes	No	Central lab
-2 (3 rd)	Yes	Yes	Not used

In addition, if at least 1 central laboratory value is used in the baseline calculation, the reference range of the central laboratory will be used to determine the toxicity grade according to National Cancer Institute (NCI) Common Terminology Criteria for Adverse Events (CTCAE). If the baseline value is calculated from local laboratory values only, then the reference range of the local laboratory will be used.

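### SAP 3.4.2 drops platelet count, hemoglobin, creatinine, LDH and haptoglobin from the laboratory safety tables that protocol 13.2.9.3 plans without exception, and does not record the departure

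*SAP*

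**What the plan says.** Protocol 7.3.1 makes safety a co-primary endpoint: "Safety as assessed by adverse events (AEs), vital signs, ECGs, and clinical laboratory tests (includes patients with HSCT-TMA, aHUS, and TTP". Protocol 13.2.9.3 then plans three kinds of laboratory table: actual values and change from baseline by visit, patients outside the reference range after baseline, and grade shifts. On the last it says: "Shift tables comparing the baseline National Cancer Institute (NCI) CTCAE grade to the worst post baseline grade will be provided by dose and disease". No test is exempted from any of the three.

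SAP 3.4.2 carries over all three kinds of table. For patients with abnormal values it reads: "Patients with laboratory values outside of the normal reference range at any post-baseline assessment will be summarized by dose and disease". The by-visit summaries and the grade shifts are likewise kept from the protocol. The paragraph then ends with a restriction that the protocol does not have: "These laboratory summary tables will exclude the laboratory tests that are the efficacy endpoints (Section 2.1". The same section names the tests concerned when it sets the rule on central laboratory data: "except for those as secondary endpoints (platelet count, LDH, creatinine, hemoglobin and haptoglobin".

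SAP 2.5, on the baseline platelet count, says that if any central value enters the average, "the reference range of the central laboratory will be used to determine the toxicity grade".

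SAP Section 4, whose title covers deviations from the protocol, does not mention the exclusion.

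**The concern.** The five excluded tests are the ones the trial uses to follow thrombotic microangiopathy. The protocol promises a tabulated safety account of laboratory results in every disease. Under the SAP, that account omits platelet count, hemoglobin and creatinine, although protocol 12.1.1 lists all three among its laboratory assessments.

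A mean change can look favourable while some patients get worse. Out-of-range counts and baseline-to-worst shifts are the tables that show how many patients deteriorated and how far. Without them, a reader of the study report must rebuild that count from listings, for a component of a co-primary endpoint.

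**Working it through.** No sample-size or error-rate figure bears on this point. The check compares the texts, counts patients, and asks whether another planned output replaces the missing tables.

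**1. Same tables, different scope.** The shift-table sentences in protocol 13.2.9.3 and SAP 3.4.2 are almost identical, as are those on by-visit summaries and out-of-range counts. The only substantive difference in scope is the SAP's closing exclusion. Its wording points back to the laboratory summary tables as a group, so it covers all three kinds.

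**2. Which tests.** SAP 2.1 makes platelet count, LDH, haptoglobin, hemoglobin and creatinine secondary endpoints (change from baseline). Platelet count, LDH and creatinine also enter the response definition. These are the five tests named in SAP 3.4.2.

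**3. Are they safety tests in the protocol?** Creatinine (chemistry), hemoglobin and platelet count (hematology) are listed in 12.1.1. LDH and haptoglobin are not in that list, but the visit procedures (for example 10.1.2.5) group them under clinical laboratory tests. The conflict is therefore firm for three tests and somewhat weaker for two.

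**4. Patients affected (SAP Table 1).**

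- aHUS: 3 + 2 + 2 + 14 + 4 = 25
- TTP: 1 + 4 = 5
- HSCT-TMA: 2 + 22 + 4 = 28, which agrees with the approximately 28 in SAP 1.3
- Total: 25 + 5 + 28 = 58
- Outside the efficacy population: 25 + 5 = 30, and 30/58 = 51.7%

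**5. Does another output give the same information?**

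| Output | What it gives for the five tests | What it lacks |
|---|---|---|
| Secondary efficacy analyses (SAP 2.8.2.2.4) | Time-weighted average and modelled mean change | FAS only, so HSCT-TMA only; no worst value, grade or range count |
| Plots (SAP 2.8.2.1, 2.8.2.2.4) | Individual platelet and LDH plots; all five tests over time in HSCT-TMA | No counts; not planned for aHUS or TTP |
| AE tables (SAP 3.4.1) | Worsening reported as an AE, by maximum severity, dose and disease | Changes that do not reach AE status |
| Listings (SAP 3.4.2) | Every central and local result | No summary |
| Marker summary for aHUS and TTP (protocol 13.2.8) | Exploratory summary by disease | Tests not named; no grades or range counts promised |

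The efficacy analyses have a further limit. SAP 2.1 drops platelet counts taken on the day of a platelet transfusion or in the 2 days after it. It drops hemoglobin taken on the day of an RBC or whole-blood transfusion or in the 6 days after it. A low value that prompts a transfusion the same day is therefore not used.

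**6. Internal consistency.** SAP 2.5 sets the range for grading the baseline platelet count. With platelet shifts excluded, no visible table uses that grade.

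**The case against.** The strongest reply is that little is lost. AEs are graded by CTCAE (protocol 12.2.2) and tabulated by maximum severity. A fall in platelets or hemoglobin that needs intervention can qualify as an AE under protocol 12.1, and 12.3.1 also counts laboratory findings that the investigator considers clinically significant. For HSCT-TMA there are plots, and the relapse rule in SAP 2.8.2.2.3 captures one form of worsening in responders. For aHUS and TTP, protocol 13.2.8 plans a marker summary, SAP 3.1 says these patients will be summarized by dose, and SAP 3.2.3 tabulates baseline hemoglobin and creatinine. The five tests also measure the disease itself. HSCT-TMA eligibility requires a platelet count below 150,000/µL and a doubling of creatinine, so out-of-range counts mix disease with drug effect. Finally, protocol 13.2 calls itself an overview and requires an amendment only when a principal feature changes.

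Much of this stands, and it rules out three stronger readings that a reader might draw from the exclusion:

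- **Worsening of these tests is invisible as safety.** It is not: events that reach AE status are tabulated and every result is listed. What is missing is tabulation of laboratory values and grades.
- **aHUS and TTP patients get no summary of creatinine or hemoglobin.** The documents do not show this. The markers in protocol 13.2.8 are not enumerated, and protocol 10.2.1.1 gives hemoglobin and creatinine among its examples of signs of TMA improvement. SAP 2.8.3 is redacted, although SAP 3.3 points to it for PK, PD and immunogenicity.
- **All five tests lose a CTCAE shift table.** The documents do not say that each of the five has a CTCAE grade.

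Nor do the documents establish that an amendment was required. But none of these points supplies an out-of-range count or a worst-grade shift. Confounding by disease activity is a reason to read such tables with care, not to omit them without saying so.

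**Conclusion.** The point holds as a conflict between protocol 13.2.9.3 and SAP 3.4.2 that touches a co-primary safety component and is not recorded in SAP Section 4. No visible analysis gives out-of-range counts or baseline-to-worst grade shifts for the five tests in any of the 58 patients. For 30 of them (51.7%) the efficacy analyses offer no cover at all. The case is firmest for platelet count, hemoglobin and creatinine.

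This rests on two assumptions: that the exclusion applies to all three kinds of table, as its wording indicates, and that the redacted SAP 2.8.3 holds no safety laboratory tables. It is an undisclosed narrowing of the safety reporting and should be corrected. It does not show that harm would go unreported.

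**What to change.** Delete the exclusion sentence in SAP 3.4.2, or limit it to by-visit mean-change tables that would duplicate the HSCT-TMA efficacy analyses. In either case, in the Safety Analysis Set by disease and dose:

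- Keep CTCAE baseline-to-worst shift tables for platelet count, hemoglobin and creatinine, and for LDH and haptoglobin only where a grade exists.
- Keep out-of-range tables for all five tests.
- Use all values, including those near transfusions.
- State which creatinine baseline the shift table uses. Protocol 13.2.1 takes the maximum from TMA diagnosis to 4 weeks after the first dose, while SAP 2.5 takes the last value before the first dose. Under the protocol's definition, an early rise would become part of the baseline.

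If the sponsor prefers to keep any wider exclusion, record and justify it in SAP Section 4.

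The cost is one changed SAP sentence, a line on the creatinine baseline and a few more tables, with no new data. The added tables need a note that these tests also reflect disease activity and transfusion.

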3.4.3. Vital Signs

Summary statistics for actual values and change from baseline will be tabulated for vital signs by dose, disease, and scheduled visit. Vital signs may also be presented graphically.

3.4.4. Electrocardiogram

The ECG parameters (heart rate, PR interval, QRS interval, QT interval, and QTc interval) at each time point as well as the change from baseline will be summarized with descriptive statistics by dose and disease. These parameters will be determined electronically by the ECG machine at the clinical site. QTc interval will be calculated using Fridericia's formula and will be categorized into the following groups: ≤ 450 , $> 450 - 480$, $> 480 - 500$ and > 500 ms.

Categorized QTc intervals will be summarized with frequency and percentage by time point, dose, and disease. Shift tables comparing the baseline categorized QTc interval to the maximum post-baseline categorized QTc interval will be provided by dose and disease. In addition, increase of > 30 ms and > 60 ms from baseline in QTc interval will be summarized with frequency and percentage by study time point, dose, and disease.

The overall ECG assessment will be reported as "Normal," or "Abnormal – not clinically significant" or "Abnormal – clinically significant" with respect to relevant abnormalities by the investigator. Shifts from the baseline ECG assessment to the worst post-baseline ECG assessment will be tabulated by dose and disease. A listing of specific ECG abnormalities will be provided.

4. PROTOCOL AND STATISTICAL ANALYSIS PLAN AMENDMENTS AND DEVIATIONS FROM THE PROTOCOL

SAP v1.1 incorporates changes made in Protocol Amendment [REDACTED]. These changes include the sample size of Stage 2 and the addition of Stage 3. The sample size determination was also clarified in SAP v1.1 and the statistical analyses remained the same. In addition, the dose of 4 mg/kg weekly for Stage 2 was selected based on the safety review of Stage 1 data.

SAP v2.0 incorporates changes made in Protocol Amendment [REDACTED]. The majority of the changes are due to the addition of the study endpoints and additional data collection for the HSCT-TMA patients.

REFERENCES

